Eosinophils	Alkaline phosphatase	Nitrites	HIV Ab ⁱ
Platelet count	CPK	Microscopic	QuantiFERON-TB Gold
	Sodium	examination,	High sensitivity CRP
	Potassium	if needed	(hs-CRP) ^f
	Bicarbonate/CO ₂		FSHi ^g
	Chloride		Local Lab Tests:
	Calcium		Urine pregnancy test ^h
	Inorganic phosphate		
	Uric acid		
	Total protein		
	Glucose		
	Cholesterol		
	LDL-C		
	HDL-C		
	Triglycerides		

ALT = alanine aminotransferase; AST = aspartate aminotransferase; bHCG = beta human chorionic gonadotropin; BUN = blood urea nitrogen; CPK = creatine phosphokinase; DNA = deoxyribonucleic acid; FSH = Follicle-Stimulating Hormone; HBc Ab = hepatitis B core antibody; HBs Ab = hepatitis B surface antibody; HBs Ag = hepatitis B surface antigen; HBV = hepatitis B virus; HCV Ab = hepatitis C virus antibody; HDL-C = high-density lipoprotein cholesterol; HIV = human immunodeficiency virus; hsCRP = high sensitivity C-reactive protein; INR = international normalized ratio; LDL-C = low-density lipoprotein cholesterol; PCR = polymerase chain reaction; pH = RBC = red blood cell; RNA = ribonucleic acid; TB = tuberculosis; WBC = white blood cell

- Minimum 8-hour fast. If a subject is not able to fast when necessary, due to unforeseen circumstances, the non-fasting status will be recorded in study source documentation.
- A urine dipstick macroscopic urinalysis will be completed by the central laboratory at all required visits. A microscopic analysis will be performed in the event the dipstick results show leukocytes, nitrite, protein, ketones, or blood greater than negative or glucose greater than normal.
- INR will only be measured if ALT and/or AST > 3 × ULN.
- A serum pregnancy test will be performed for all female subjects at the Screening Visit and if postbaseline urine pregnancy test turns positive.

Table 4. Clinical Laboratory Tests (Continued)

- e. At Screening only. For Japan only: for subjects with HBs Ab+ and/or HBc Ab+ at Screening, the HBV-DNA PCR test should be performed again at Week 12 and Week 24. In cases where the recurrence of HBV-DNA is observed, the subject should be discontinued from the study drug. Retesting at Week 12 and Week 24 is not necessary with subjects that have a history of HBV vaccine and are HBs Ab+.
- f. The hs-CRP results starting from Baseline (Day 1) will not be reported to the Sponsor, Investigator, study site personnel, and the subject. For safety evaluations of signs and symptoms of infection and management of adverse events, the investigator may locally test procalcitonin. Results of tests such as hsCRP, serum amyloid A and procalcitonin may be blunted in subjects taking a JAK inhibitor, thereby limiting the clinical utility of these tests in the setting of a possible safety assessment or adverse event management. Any hsCRP, CRP, serial serum amyloid A, or serial procalcitonin local tests reported to the investigator will be recorded as protocol deviations.
- g. At screening for female subjects < 55 years old.
- h. A urine pregnancy test will be performed for all female subjects at the Baseline Visit prior to the first dose of study drug and all subsequent visits. If the baseline urine pregnancy test performed at the site is negative, then dosing with study drug may begin. If the baseline urine pregnancy test performed at the site is positive, dosing with study drug must be withheld and a serum pregnancy test is required. The serum pregnancy test will be sent to and performed by the central laboratory. If the serum pregnancy test is positive, study drug must be withheld and the subject must be discontinued from the study. In the event a pregnancy test comes back borderline, a repeat test is required. If a urine pregnancy test postbaseline is positive, study drug needs to be temporarily discontinued and a serum pregnancy test is required. The serum pregnancy test will be sent to and performed by the central laboratory. If the serum pregnancy test is positive, study drug must be permanently discontinued.
- i. Anti-HIV Ab will be performed at Screening. The Investigator must discuss any local reporting requirements to local health agencies with the subject. The site will report confirmed positive results to their health agency per local regulations, if necessary. If a subject has a confirmed positive result, the Investigator must discuss with the subject the potential implications to the subject's health and subject should receive or be referred for clinical care promptly. This testing is to be done at the central lab. A subject will not be eligible for study participation if test results indicate a positive HIV infection. AbbVie will not receive results from the testing and will not be made aware of any positive result.

Hepatitis Screen:

All subjects will be tested for the presence of HBV and HCV at Screening.

Hepatitis B:

Subjects will be tested for the presence of HBV at screening using the following tests:

HBs Ag

HBc Ab/anti-HBc

[figure not shown]
HBs Ab/anti-HBs (Hepatitis B surface antibody)

A positive result for HBs Ag will be exclusionary.

A negative result for HBs Ag will be tested (automatic reflex testing) for core antibodies (HBc Ab) and surface antibodies (HBs Ab).

- A negative test result for HBc Ab does **not** require HBV DNA PCR qualitative testing and the subject may be enrolled (Figure 2, Scenarios A and B). For a subject who has had a HBV vaccination (should document in the medical history), a positive test result for HBs Ab is expected and the subject may be enrolled (Figure 2, Scenario B).*
- A positive test result for HBc Ab requires HBV DNA PCR testing (automatic reflex testing) (Figure 2), (Scenarios C and D).
 - A positive result for HBV DNA or a result that exceeds detection sensitivity will be exclusionary.
 - A subject with a negative result for HBV DNA testing may be enrolled.
 - For Japan only: for subjects with HBs Ab+ and/or HBc Ab+ at Screening, the HBV-DNA PCR test should be performed again at Week 12 and Week 24. In cases where the recurrence of HBV-DNA is observed, the subject should be discontinued from the study drug. Retesting at Week 12 and Week 24 is not necessary with subjects that have a history of HBV vaccine and are HBs Ab+.

Figure 2. Criteria for HBV DNA PCR Qualitative Testing

* For subjects who have had a HBV vaccination (should document in the medical history), a positive test result for HBs Ab is expected and these subjects may be enrolled.

Hepatitis C:

All subjects will be tested for the presence of Hepatitis C Virus antibodies (HCV Ab) at Screening. Samples positive for HCV Ab require PCR qualitative testing for HCV RNA. Any HCV RNA PCR result that meets or exceeds detection sensitivity will be exclusionary. Subjects with a history of treated HCV infection may be allowed to enroll if documentation of effective treatment is available and no evidence of HCV is detected by HCV RNA PCR.

TBNK Assessment By Immunophenotyping

Blood samples will be collected at the Baseline, Week 8, Week 16, and Week 20, visits and will be utilized to assess effects of JAK inhibition on certain leukocyte subsets, including T (CD4+ and CD8+) cells, B (CD19+) cells, natural killer (NK) cells, and natural killer-T (NKT) cells. Instructions for the preparation and shipment of the samples will be provided in the laboratory manual.

HIV

Subjects with HIV infection are excluded from study participation. HIV testing will be performed at Screening. This testing is to be done at the central lab. The Investigator must discuss any local reporting requirements to local health agencies with the subject. The site will report confirmed positive results to their health agency per local regulations, if necessary. If a subject has a confirmed positive result, the Investigator must discuss with the subject the potential implications to the subject's health and subject should receive or be referred for clinical care promptly. A subject will not be eligible for study participation if the test results indicate a positive HIV infection. AbbVie will not receive results from the testing and will not be made aware of any positive result.

Randomization/Drug Assignment

All Screening laboratory results must be reviewed, signed, and dated by the Principal Investigator or Sub-investigator prior to the Baseline Visit. Subjects will not be enrolled into the study if laboratory or other Screening result abnormalities are deemed clinically significant by the Principal Investigator or Sub-investigator.

Subjects will be eligible for randomization if they continue to meet all of the selection criteria (Section 5.2) at Baseline and are willing to continue in the study.

In Period 1, at the Baseline visit, subjects will be randomized in a 1:1.1:1 ratio using interactive response technology (IRT) to receive double-blind study drug in one of the following treatment groups:

- Group 1: ABT-494 7.5 mg QD for 16 weeks
- Group 2: ABT-494 15 mg QD for 16 weeks
- Group 3: ABT-494 30 mg QD for 16 weeks
- Group 4: Matching Placebo for 16 weeks

Randomization will be stratified by geographic region (US/PR/Canada, EU/AUS, and Japan). Enrollment in Japan will be capped at 10% of subjects (approximately 4 subjects per group).

In Period 2, at the Week 16 visit, all subjects will be re-randomized in a 1:1 ratio using interactive response technology (IRT) to receive double-blind study drug in one of the following treatment groups:

- Subjects from Group 1 in Period 1: ABT-494 7.5 mg QD or matching placebo for 24 weeks
- Subjects from Group 2 in Period 1: ABT-494 15 mg QD or matching placebo for 24 weeks
- Subjects from Group 3 in Period 1: ABT-494 30 mg QD or matching placebo for 24 weeks
- Subjects from Group 4 in Period 1: ABT-494 30 mg QD or matching placebo for 24 weeks

During Period 2, starting at the Week 20 visit, subjects re-randomized to placebo, ABT-494 7.5 mg QD or ABT-494 15 mg QD will be reassigned in a blinded manner to ABT-494 30 mg QD if at any visit their response is < EASI 50. These subjects will continue on ABT-494 30 mg QD for the remainder of the study.

See Section 5.5.3 for details.

Study Drug Dispensing, Dosing, and Compliance

Study drug and Dosing Diary will be dispensed to subjects beginning at Baseline (Day 1) and as specified in Table 2. The first dose of study drug will be administered after all other Baseline (Day 1) procedures are completed. Subjects will maintain an electronic dosing diary for all study medication administered outside of the study visit, (e.g., at home) to capture dosing dates and times. At all visits, except Baseline, Week 2, 4-week follow-up visit after topical corticosteroid rescue in Period 2, and the 30-day follow-up visit, the site personnel will review the electronic diary data, returned study drug kits, and

empty study drug packaging to verify compliance. Electronic diary data stops at the Week 40 visit.

(Refer to Section 5.5 for additional information.)

Actigraphy Device

During the Screening Visit, subjects will be dispensed two actigraphy devices and will be trained on how and when to wear the devices by site staff. Subjects will be instructed to wear two actigraphy watch-type devices (one on each wrist) at bedtime daily during their whole daily rest (sleep) period (see Section 10.2 for more detail). Data will be collected from the day of the Screening visit through the Week 16 visit (see Table 2 for visits requiring data download).

5.3.1.2 Collection and Handling of Optional and Mandatory Samples for Exploratory Research and Validation Studies

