Blood samples for exploratory research and validation studies (optional for some sites – see table for optional samples below) ^w		X	X	X			X	X						
Skin biopsies for exploratory research and validation studies (optional for some sites – see Table 3 for optional samples below) ^w		X		X			X							
Study Drug Dispensing/Administration		X		X	X	X	X	X	X	X	X	X ^z		
Dispense hand-held ePRO (includes subject diary) and actigraphy device	X													
Subject Diary Review			X	X	X	X	X	X	X	X	X			

Table 2. Study Activities (Continued)

- ADerm-IS = Atopic Dermatitis Impact Scale; ADerm-SS = Atopic Dermatitis Symptom Scale; BL = Baseline Visit; BSA = body surface area; CBC = complete blood count; D = Day; DLQI = Dermatology Life Quality Index; EASI = Eczema Area and Severity Index; ECG = electrocardiogram; F/U = Follow-Up; HBV = hepatitis B virus; HCV = hepatitis C virus; HIV = human immunodeficiency virus; hsCRP = high-sensitivity C reactive protein; IGA = Investigator's Global Assessment; MOS = Medical Outcomes Study; NRS = Numerical Rating Scale (for pruritus); PD = Premature Discontinuation; PGIS = Patient Global Impression of Severity; PK = pharmacokinetics; POEM = Patient Oriented Eczema Measure; PPD = purified protein derivative; PtGA = Patient's Global Assessment; SAE = serious adverse event; SCORAD = Scoring atopic dermatitis; TB = tuberculosis; Wk = Week
- a. This visit is 30 days (\pm 3 days) after last dose of study drug. For those subjects who prematurely discontinue the study, if the subject is willing, a 30-day follow-up visit (or phone call if a visit is not possible) may occur to determine the status of any ongoing AEs/SAEs or the occurrence of any new AEs/SAEs. If a subject is discontinued from study drug, the procedures outlined for the Premature Discontinuation visit (PD visit) should be completed as soon as possible, preferably within 2 weeks of study drug discontinuation.
 - b. The Baseline visit procedures will serve as the reference for all subsequent visits with the exception of the ECG which will be obtained at Screening only and used as the baseline reference.
 - c. Obtain prior to performing any study-related procedures.

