Only qualified personnel must perform an assessment of the CXR. The Principal Investigator will indicate the clinical significance of any findings and will sign and date the report. In the assessment of the CXR, the Principal Investigator or their delegate must indicate the presence or absence of (1) calcified granulomas, (2) pleural scarring/thickening, and (3) signs of active TB. If the CXR demonstrates changes suggestive of previous TB (e.g., calcified nodule, fibrotic scar, apical or basilar pleural thickening) or other findings that are clinically significant, the Investigator must contact the AbbVie Therapeutic Area Scientific Director who will discuss with the AbbVie Medical Director before enrolling the subject.

12-Lead ECG

A resting 12-lead ECG will be performed at the designated study visits as specified in [Table 2](#). A qualified physician will interpret the clinical significance of any abnormal

finding, sign, and date each ECG. ECG with QT interval corrected for heart rate using Friedericia's correction formula (QTcF) should be reported (or calculated) and documented in the source documents and later transcribed on to the appropriate eCRF if QTcF prolongation is observed. In these cases, the baseline QTcF will need to be entered into the appropriate eCRF for comparison as well. In addition, any clinically significant findings will be documented in the source documents and later transcribed on to the appropriate eCRF. Each signed original ECG will be monitored by the responsible site monitor and kept with subject's source documents onsite.

For subjects with a normal ECG taken within 90 days of Screening, a repeat ECG at Screening will not be required, provided source documentation is available. If there are other findings that are clinically significant, the Investigator must bring this to the attention of the AbbVie Therapeutic Area Scientific Director who will discuss with the AbbVie Medical Director and provide a recommendation before the subject can be enrolled.

Subjects can have a repeat ECG at any time during the study as warranted, based on the opinion of the Investigator.

Height and Weight

Height will be measured at the Screening Visit only (with shoes off). Body weight will be measured at all scheduled visits, as specified in [Table 2](#). All measurements will be recorded in metric units where applicable.

Vital Signs

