ECG Abnormality: Subjects must be discontinued from study drug for an ECG change considered clinically significant OR a confirmed absolute QTcF value > 500 msec.

Management of Select Laboratory Abnormalities: For any given confirmed laboratory abnormality (confirmation by repeat testing with a new sample), the Investigator should assess the subject, apply the standard of care for medical evaluation and treatment following any local guidelines. Specific toxicity management guidelines for abnormal laboratory values are described in [Table 6](#) and may require an appropriate supplemental eCRF be completed.

Table 6. Specific Toxicity Management Guidelines for Abnormal Laboratory Values

Laboratory Parameter	Toxicity Management Guideline
Hemoglobin	
 • If hemoglobin < 8 g/dL interrupt study drug dosing and confirm by repeat testing with new sample • If hemoglobin decreases \geq 3.0 g/dL from baseline, without an alternative etiology, interrupt study drug dosing and confirm by repeat testing with new sample. • If hemoglobin decreases \geq 3.0 g/dL from baseline and an alternative etiology is known, the subject may remain on study drug at the investigator's discretion. • If confirmed, continue to withhold study drug until hemoglobin value returns to normal reference range or its baseline value.
Absolute neutrophil count (ANC)	
 • If confirmed < 1000/μL by repeat testing with new sample, interrupt study drug dosing until ANC value returns to normal reference range or its baseline value. • Discontinue study drug if confirmed < 500/μL by repeat testing with new sample.
Absolute lymphocyte counts (ALC)	
 • If confirmed < 500/μL by repeat testing with new sample, interrupt study drug dosing until ALC returns to normal reference range or its baseline value.
Total white blood cell count	
 • If confirmed < 2000/μL by repeat testing with new sample, interrupt study drug dosing until white blood cell count returns to normal reference range or its baseline value.
Platelet count	
 • If confirmed < 50,000/μL by repeat testing with new sample, interrupt study drug dosing until platelet count returns to normal reference range or its baseline value.

Table 6. Specific Toxicity Management Guidelines for Abnormal Laboratory Values (Continued)

Laboratory Parameter	Toxicity Management Guideline

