**Table 15. AESI for Upadacitinib with SMQs/CMQs Searches**

AESI	Type of MedDRA Query	Broad or Narrow Search	SMQ/CMQ Search Criteria
Serious Infections	CMQ		"Infections" – Subset for SAEs
Opportunistic Infection	CMQ		"Opportunistic Infection"
Malignancy	SMQ	Narrow	"Malignancies"
Non-Melanoma Skin Cancer (NMSC)	SMQ	Broad	Skin Malignant tumours (Broad SMQ) removing Melanoma CMQ
Malignancy excluding NMSC			Malignancy Narrow SMQ and removing NMSC output
Lymphoma	SMQ		"Malignant Lymphomas"
Hepatic Disorder	SMQ	Narrow	"Drug Related Hepatic Disorders"
Gastrointestinal Perforations	SMQ	Narrow	"Gastrointestinal Perforation"
Anemia	CMQ		"Non-Hemolytic and Non-Aplastic Anemias"
Neutropenia	CMQ		"Hematological Toxicity – Neutropenia"
Lymphopenia	CMQ		"Hematological Toxicity – Lymphopenia (Veliparib Product Specific)"
Herpes Zoster	CMQ		"Herpes Zoster"
Rhabdomyolysis/myopathy	SMQ	Narrow	"Rhabdomyolysis/Myopathy"
Creatine Phosphokinase (CPK Elevation)	PT		Search only for the PT of "Blood creatine phosphokinase increased"
Renal Dysfunction	SMQ	Narrow	"Acute Renal ,Failure"
Tuberculosis	CMQ		"Tuberculosis"
Adjudicated cardiovascular events a	Output from CAC		
Cardiac Arrhythmias	SMQ	Narrow	"Torsade de pointes/QT Prolongation" "Tachyarrhythmias"

a. Reviewed and adjudicated by an independent Cardiovascular Adjudication Committee in a blinded manner.

Additional AEs may be considered for tabulation/summary based on recommendations from Clinical and Safety as deemed appropriate.

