#### 11.5 Analysis of ECG Parameters

ECG is collected at baseline visit, and Week 16. ECG findings will be summarized by treatment group for each parameter and visit. Summaries will include n (%) of patients in following categories:

- Normal
- Abnormal – Not Clinically Significant
- Abnormal – Clinically Significant
- Unable To Evaluate
- Missing

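### QTcF reaches the database only when prolonged, and SAP 11.5 gives only category counts, so QTcF change by dose versus placebo cannot be estimated without bias

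*Protocol*

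**What the plan says.** **Capture.** Under 12-Lead ECG in Protocol 5.3.1.1, a physician interprets each ECG. QTcF is reported or calculated and documented in source, then "later transcribed on to the appropriate eCRF if QTcF prolongation is observed". The next sentence treats baseline the same way: "In these cases, the baseline QTcF will need to be entered into the appropriate eCRF for comparison as well". Prolongation is not defined there. Signed originals are monitored and "kept with subject's source documents onsite"; no central reading is described.

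**Schedule.** Protocol Table 2 marks ECGs at Screening and Week 16 only. Its footnote b makes an exception for the "ECG which will be obtained at Screening only and used as the baseline reference". A normal ECG from within 90 days of Screening may stand in for the Screening ECG. SAP 11.5 says "ECG is collected at baseline visit, and Week 16".

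**Analysis.** SAP 11.5 summarises ECG findings by treatment group, parameter and visit, then specifies the output: "Summaries will include n (%) of patients in following categories", namely normal, abnormal not clinically significant, abnormal clinically significant, unable to evaluate and missing. Protocol 8.1.6.3 has ECG in its title, but its change-from-baseline text covers only laboratory data and vital signs. SAP 11.1 leaves ECG out of its list of safety analyses.

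**Where QTcF or ECG is used.** ECG is one of the measures in the SAP's secondary safety objective (4.1). QTcF above 500 msec is part of exclusion criterion 11, and "a confirmed absolute QTcF value > 500 msec" requires stopping study drug (Protocol 6.1.7).

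**The concern.** The QTcF values in the database are selected on the outcome, and each site decides for itself what counts as prolonged. A mean change computed from them describes only subjects with high readings. Comparing arms within that subset compares groups chosen after treatment, so randomisation no longer protects the comparison. Site-dependent capture also makes counts unreliable for any threshold at which sites might disagree, and for increases from baseline.

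Week 16 is the only scheduled on-treatment ECG and closes the randomised dose-versus-placebo period, so no later scheduled ECG could replace it. The SAP already gives vital signs a change from baseline with a confidence interval for each dose versus placebo (11.4.2), and laboratory values an ANOVA comparison (11.3.2.1). QTcF has a numeric stopping rule but gets neither.

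**Working it through.** The plan states no ECG sample size, power or precision, so there is no figure to reproduce. Two questions can be worked through.

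**1. What do recorded-only data show?**

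Assumptions, none from the documents: baseline QTcF is normal with mean 405 and SD 18, or mean 410 and SD 20 msec. The SD of change (s) is 10, 15 or 20 msec, independent of baseline. A value is entered if Week 16 QTcF exceeds a cut-off c of 450 or 480 msec. The true drug effect (e) is 0 on placebo and 10 msec on active. Each arm has 40 subjects (Protocol 8.2).

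With baseline mean m and SD b:
- SD of Week 16 QTcF: σ = √(b² + s²)
- z = (c − m − e)/σ
- expected number recorded = 40 × (1 − Φ(z))
- mean change among those recorded = e + (s²/σ) × φ(z)/(1 − Φ(z))

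Worked case: m = 410, b = 20, s = 15, c = 450, so σ = √(400 + 225) = 25 and s²/σ = 225/25 = 9.

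| | Placebo (e = 0) | Active (e = 10) |
|---|---|---|
| z | 40/25 = 1.6 | 30/25 = 1.2 |
| Expected number recorded | 40 × 0.0548 = 2.2 | 40 × 0.1151 = 4.6 |
| φ(z)/(1 − Φ(z)) | 2.024 | 1.688 |
| Mean change among recorded | 9 × 2.024 = 18.2 msec | 10 + 9 × 1.688 = 25.2 msec |

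Placebo shows a rise of 18 msec when the true change is zero, and the between-arm difference is 7.0 instead of 10 msec.

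Over the six combinations with a 450 msec cut-off:
- about 0.6 to 3.2 placebo and 1.8 to 5.8 active subjects are recorded per 40
- the spurious placebo rise is about 10 to 31 msec
- the apparent difference is about 5 to 8 msec instead of 10

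At 480 msec, fewer than one subject per arm is expected. If a site judged prolongation by the rise from baseline instead, selection would act directly on the change.

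**2. What precision would full capture give?**

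Half-width of the 95% interval = t(0.975; 4n − 4) × SD × √(2/n), from a four-arm model with pooled variance. For n = 40: t = 1.975 on 156 degrees of freedom and √(2/40) = 0.2236. For n = 35 (an assumed loss of 5 per arm): t = 1.978 on 136 degrees of freedom and √(2/35) = 0.2390.

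| Assumed SD of change | n = 40 per arm | n = 35 per arm |
|---|---|---|
| 12 msec | 5.3 | 5.7 |
| 16 msec | 7.1 | 7.6 |
| 20 msec | 8.8 | 9.5 |

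**Volume of data entry:** at most 2 ECGs × 160 subjects = 320 values.

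**The case against.** **The plan never promises a QTcF estimate.** Protocol 8.1.6.3 limits change-from-baseline summaries to laboratory data and vital signs, and a categorical ECG table does address the SAP objective. This stands: the documents do not contradict themselves here, and the point is an improvement. How much it matters also depends on earlier QT evidence for the drug, which the documents do not give.

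**SAP 11.5 says findings are summarised for each parameter.** That wording leaves some room, but the only outputs listed are category counts, and QTcF values are not in the database for most subjects.

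**A reader might infer that no share above any threshold can be reported.** The documents do not support that. A value above 500 msec is prolonged on any reasonable reading, so it would be entered with its baseline. If confirmed, it also forces discontinuation of study drug, and SAP 8.0 summarises reasons for discontinuation. The gap is in lower thresholds and increases from baseline, and in the absence of a table for the 500 msec count.

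**A reader might infer that measured QTcF determines a special-interest event.** It does not. SAP Table 15 finds Cardiac Arrhythmias through MedDRA queries, one of them "Torsade de pointes/QT Prolongation", applied to coded adverse event terms. No QTcF value enters the definition. Equally, the query does not replace the measurement.

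**A reader might infer that full capture would rule out large QTcF effects.** The intervals above reflect sampling error only. The protocol describes a resting ECG with no replicates or central reading, and no time after dose is set at Week 16. Protocol 3.0 puts peak concentration at 2 to 4 hours and half-life at 9 to 14 hours, so an estimate at an uncontrolled time does not bound the effect at peak.

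**Nor are unrecorded values lost.** They, or the tracings from which QTcF can be calculated, remain in monitored source documents.

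**Conclusion.** The point holds as a cheap improvement. As written, the plan cannot give an unbiased mean change in QTcF for each dose versus placebo, or reliable counts below 500 msec or for increases from baseline. Values above 500 msec would be captured but are not tabulated. This conclusion follows from the capture rule and the SAP's output list, and does not depend on the assumed QTcF distributions; those only illustrate how far recorded-only data could mislead.

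Full capture would give a 95% half-width of about 5 to 9 msec per dose versus placebo at 40 per arm, on an assumed SD of 12 to 20 msec. That would be supportive safety evidence, with the limits on ECG reading and timing noted above. The efficacy analyses are not affected.

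**What to change.** 1. Enter QTcF in the eCRF for every subject with an ECG, at Week 16 and at Screening. Where a prior normal ECG replaced the Screening one, use its QTcF if reported or calculable.
2. Add to SAP 11.5 the change from baseline in QTcF by arm: ANCOVA with treatment and baseline QTcF, each dose versus placebo, with 95% confidence intervals. Report the number of subjects with both values.
3. Add counts by arm above prespecified QTcF thresholds, including the protocol's own 500 msec, and for prespecified increases from baseline.
4. Align the SAP's description of the first ECG (baseline visit) with the protocol's (Screening).

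**Cost:** transcription of up to about 320 values, one eCRF field and one table. No new ECGs are needed, no clinical rule changes, and the entry can be done retrospectively from source. The count will be lower where Week 16 ECGs are missing or a substituted prior ECG carries no usable QTcF.
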